5.7 Women of Childbearing Potential

WOCBP is defined as any woman who has experienced menarche and who has not undergone surgical sterilization (hysterectomy, bilateral tubal ligation, or bilateral oophorectomy) and is not postmenopausal.

See [Section 5.7.2](#) for detailed information regarding contraceptive requirements for WOCBP.

5.7.1 Determination of Menopause

Menopause is defined as at least 12 months of amenorrhea in a woman over age 45 in the absence of other biological or physiological causes. Women under the age of 55 years must have a documented serum FSH level > 40 mIU/mL at screening to confirm menopause.

5.7.2 Contraception

WOCBP must agree to follow instructions for method(s) of contraception for the duration of treatment with study drug plus 5 half-lives of study drug BOS161721 plus 30 days (duration of ovulatory cycle) for a total of 36 weeks after treatment completion.

Men who are sexually active with WOCBP must agree to follow instructions for method(s) of contraception for the duration of treatment with study drug plus 5 half-lives of study drug BOS161721 plus 90 days (duration of sperm turnover) for a total of 44 weeks after treatment completion.

Investigators shall counsel WOCBP and men who are sexually active with WOCBP on the importance of pregnancy prevention and the implications of an unexpected pregnancy. Investigators shall advise WOCBP and men who are sexually active with WOCBP on the use of highly effective methods of contraception. Highly effective methods of contraception have a failure rate of < 1% when used consistently and correctly.

At a minimum, patients must agree to the use of 1 method of highly effective contraception from the following:

- Male condoms with spermicide
- Hormonal methods of contraception including combined oral contraceptive pills, vaginal ring, injectables, implants, and intrauterine devices (IUDs) such as Mirena[®] by patients who are WOCBP or a male patient's WOCBP partner. Women who are partner of men who are patients participating in the study may use hormone-based contraceptives as 1 of the acceptable methods of contraception since they will not be receiving study drug.
- IUDs, such as ParaGard[®]
- Vasectomy
- Complete abstinence, defined as complete avoidance of heterosexual intercourse, is an acceptable form of contraception. Women who are abstinent while participating in the study must continue to have pregnancy tests. Acceptable alternate methods of highly effective contraception must be discussed in the event that the patient chooses to forego complete abstinence.

Azoospermic men and WOCBP who are continuously not heterosexually active are exempt from contraceptive requirements. However, they must still undergo pregnancy testing.

5.8 Deviation from Inclusion/Exclusion Criteria

Deviation from the inclusion or exclusion criteria will not be allowed. If deviation of inclusion/exclusion criteria is discovered after randomization, the investigator should contact the medical monitor for discussion. A decision will be made whether to allow a patient continue or withdrawal from the study medication.

See [Section 7.8](#) for additional details.

5.8.1 Patient Withdrawal and Replacement

See [Section 6.5](#) for reasons for removal from the trial. Withdrawn patients may be replaced during the MAD study after discussion between the principal investigator or designee and sponsor.

6 STUDY PROCEDURES

Refer to the eCRF completion guidelines for data collection requirements and documentation of study assessments/procedures.

6.1 Screening

Screening will be the same for both the MAD and POC studies.

Screening will take place from Day -28 to Day -1, and assessments may be performed over more than 1 visit. Confirmation that the most current IRB/IEC approved informed consent form (ICF) has been signed must occur before any study-specific screening procedures are performed. Procedures that are part of standard of care are not considered study-specific procedures and may be performed prior to informed consent and used to determine eligibility.

All screened patients will be assigned a unique screening number. The screening number will include a 3-digit site number and a 4-digit sequential number to identify patients from the time of screening. Only eligible patients who are confirmed by central review as meeting the inclusion/exclusion criteria, listed in [Section 5.4](#) and [Section 5.5](#) respectively, will be enrolled in the study. Screened patients who drop out of the clinical study before randomization will be recorded as screen failures. If rescreening occurs, the site will assign a new screening number.

Specific procedures at the screening visit will include:

- Medical history documentation
- Review of inclusion and exclusion criteria
 - Patient medical records must contain documentation of SLE diagnosis
 - C-SSRS
- Concomitant medication documentation
- Demographics
- Full physical examination
- Vital signs

- Chest x-ray
- Laboratory evaluations (nonfasting):
 - Hematology and clinical chemistry
 - Serology (Hepatitis B and C; HIV-1/2 combination)
 - TB test
 - CRP
 - Direct Coomb's test (if indicated)
 - CD4+ count, total IgG and IgM levels, plasma CCI, plasma CCI and CCI, whole blood for leukocyte immunophenotype; CCI
 - Serum pregnancy test (WOCBP)
 - FSH (postmenopausal women)
 - Spot urine for protein/creatinine ratio
 - Urinalysis
 - Stool sample
- 12-lead ECG
- SLE-related indices (BILAG-2004 Index, SLEDAI-2K, ACR-28 joint count, CLASI, Physician's Global Assessment (PGA) of disease activity)

Screening procedures are listed in the Schedule of Assessments ([Section 4.3](#)), and details are provided in [Section 7](#).

6.1.1 Retesting During Screening Period

A single retesting of laboratory parameters and/or other assessments during the screening period is permitted (in addition to any parameters that require a confirmatory value) only if:

- medically indicated
- there is evidence a laboratory sample was mislabeled, inadequately processed, and/or deteriorated in transit to the central laboratory

Any new result will override the previous result (ie, the most current result prior to randomization) and is the value by which study inclusion/exclusion will be assessed, as it

represents the patient's most current clinical state. This will also apply to patients who are being rescreened.

6.2 Enrollment/Randomization and Day 0 Treatment

Randomization should occur after patient eligibility for enrollment has been confirmed by the central eligibility review.

The study site will obtain a randomization number when registering the patient in IWRS. All patients will receive BOS161721 or placebo according to the kit number assigned by the IWRS randomization scheme.

After randomization, procedures include:

- PROs: CCI [REDACTED]
- C-SSRS
- Laboratory evaluations (fasting):
 - Hematology and clinical chemistry
 - Direct Coomb's test (if indicated)
 - CD4+ count, total IgG and IgM levels, plasma CCI [REDACTED], plasma CCI [REDACTED] and CCI [REDACTED], whole blood for leukocyte immunophenotype
 - ADA
 - pSTAT3 (predose [trough] samples only in Phase 2)
 - CCI [REDACTED]
 - Whole blood RNA collection
 - CCI [REDACTED]
 - See [Table 1](#) and [Table 2](#) for details of PK sampling in the MAD and POC studies
 - Urine pregnancy test will be collected on WOCBP prior to study drug administration
 - Spot urine for protein/creatinine ratio
 - Urinalysis
- Concomitant medication documentation
- Documentation of AEs and SAEs (see [Section 7.2.2.5](#) on SAE reporting requirements)

- Full physical examination
- Vital signs (prior to PK blood draw, predose, and at 1 and 2 hours postdose on Day 0)
- 12-lead ECG (prior to PK blood draw)
- SLE-related indices (BILAG-2004 Index, SLEDAI-2K, ACR-28 joint count, CLASI, PGA)
- SLICC/ACR damage index
- Study drug administration:
 - Administration of BOS161721 or placebo will take place on-site, and is discussed in [Section 8.3](#)
- Injection site reaction assessment, predose, and 2 hours postdose

Procedures on Day 0 are listed in the Schedule of Assessments ([Section 4.3](#)), and details are provided in [Section 7](#).

All patients who are enrolled, randomized, and receive study drug, or undergo study-specific procedures should re consent with any updated versions of IRB/IEC approved informed consents during study participation as applicable and per institutional guidelines.

6.3 Treatment Period/Follow-Up Visits

The following procedures will be performed as indicated in the Schedule of Assessments ([Table 1](#) and [Table 2](#)). See Schedule of Assessment tables for allowable windows for each visit.

- Targeted physical examination
- Vital signs (prior to PK blood draw)
- Concomitant medication documentation
- Documentation of AEs and SAEs (see [Section 7.2.2.5](#) on SAE reporting requirements)
- PROs: **CCI**
- Urine pregnancy tests will be collected on WOCBP prior to study drug administration
- Injection site reaction assessments will be performed predose and 2 hours postdose
- Direct Coomb's test (if indicated)
- Spot urine for protein to creatinine ratio
- Urinalysis

- CCI [REDACTED]
- Plasma CCI [REDACTED]
- PGA, BILAG-2004 Index, SLEDAI-2K, ACR-28 joint count, and the CLASI will be completed
- SLICC/ACR Damage Index will be completed at Day 180
- C-SSRS
- ECGs prior to PK blood draw
- See [Table 1](#) and [Table 2](#) for details of PK sampling in the MAD and POC studies, respectively
- Fasting hematology and chemistry assessments
- The CD4+ count and total IgG and IgM levels
- Plasma CCI [REDACTED] & CCI [REDACTED], ADA, and whole blood for leukocyte immunophenotype
- pSTAT3
- Whole blood RNA
- CRP and nAb will be assessed if patient is positive for ADA
- CCI [REDACTED]

6.4 Safety Follow-Up Visits

Safety follow-up visits will take place at Days 210, 240, and 270. These visits will include the following assessments as indicated in the Schedule of Assessments (Table 1 and Table 2):

- PROs: CCI [REDACTED]
- Documentation of AEs and SAEs (see [Section 7.2.2.5](#) on SAE reporting requirements)
- Injection site reactions
- Targeted physical examination
- Vital signs (prior to PK blood draw)
- Spot urine for protein/creatinine ratio and urinalysis
- Concomitant medication documentation

- BILAG-2004 Index, SLEDAI-2K, ACR-28 joint count, CLASI, and PGA
- Fasting clinical laboratory assessments (hematology and clinical chemistry)
- Direct Coomb's test (if indicated)
- Plasma CCI
- CCI
- pSTAT3
- 12-lead ECG (prior to PK blood draw)
- CRP
- ADA
- Whole blood RNA collection
- See [Table 1](#) and [Table 2](#) for details of PK sampling in the MAD and POC studies, respectively

6.5 Premature Discontinuation

While patients are encouraged to complete all study evaluations, they may withdraw from the study at any time and for any reason. Every effort will be made to determine why any patient withdraws from the study prematurely. If the patient is unreachable by telephone, a registered letter, at the minimum, should be sent to the patient requesting him/her to contact the clinic.

All patients who withdraw from the study with an ongoing AE or SAE must be followed until the end of study or until the event is resolved or deemed stable, respectively.

If a patient withdraws prematurely after dosing, an end of treatment (EOT) visit should be performed (Day 180) and a last follow-up visit 90 days after dosing should be scheduled (Day 270). Safety follow-up visit procedures based on the Schedule of Assessments (see [Section 6.4](#)).

Patient participation may be terminated prior to completing the study and the reason recorded as follows:

- AE/SAE
- Protocol deviation
- Lost to follow-up
- Patient withdraws consent at their own request

- Investigator decision
- Decision by sponsor (other than AE/SAE, protocol deviation, or lost to follow-up)

Withdrawn patients may be replaced after discussion between the investigator or designee and sponsor.

7 ASSESSMENTS

Every effort should be made to ensure that the protocol required tests and procedures are completed as described. However, it is anticipated that from time to time there may be circumstances, outside of the control of the investigator, which may make it unfeasible to perform the test. In these cases, the investigator will take all steps necessary to ensure the safety and wellbeing of the patient. When a protocol required test cannot be performed the investigator will document the reason for this and any corrective and preventive actions which he/she has taken to ensure that normal processes are adhered to as soon as possible. All protocol violations are entered directly into the eCRFs.

7.1 Medical History, Demographic and Other Baseline Information

The medical history comprises:

- General medical history
- Documentation of SLE diagnosis
- Historical medication therapy for SLE

The following demographic information will be recorded:

- Age
- Ethnic origin (Hispanic/Latino or not Hispanic/not Latino)
- Race (White, American Indian/Alaska Native, Asian, Native Hawaiian or other Pacific Islander, Black/African American)
- Height (without shoes, in cm)
- Body weight, without shoes (kg)
- Body mass index (BMI [kg/m²])

Other baseline characteristics will be recorded as follows:

- Concomitant medication documentation (see [Section 5.6](#))
- Status of child bearing potential and contraception

7.2 Safety Assessments

7.2.1 Laboratory Assessments

Laboratory tests will be performed at times defined in the Schedule of Assessments (Section 4.3). Patient eligibility will be determined based on these tests at screening. Unscheduled clinical labs may be obtained at any time during the study to assess any perceived safety concerns.

A central laboratory will be used (with the exception of urine pregnancy tests and stool analysis) to ensure accuracy and consistency in test results. The central laboratory will transmit all results for protocol tests, scheduled and unscheduled, to the clinical data base. Laboratory/analyte results that could unblind the study (ie, biomarker results) will not be reported to investigative sites. Urinalysis will be performed on midstream, clean catch specimens. Some biomarkers listed above will not be drawn at some sites due to geographical logistical challenges. See the laboratory manual for details.

Endpoint analyses will be based on changes from baseline assessments at Days 120 and 210.

Table 3. Laboratory Tests

Hematology	Chemistry	Urinalysis	Other Safety Tests
Hemoglobin	BUN	pH	Spot urine for protein/creatinine ratio
Hematocrit	Creatinine	Glucose (qual)	FSH ^b
RBC count	Glucose (fasting)	Protein (qual)	Urine pregnancy test ^c
RDW	Calcium	Blood (qual)	QuantiFERON [®] -TB Gold In-Tube test (QFT-G)
MCV	Sodium	Ketones	Serology ^d (Hepatitis B and C; HIV-1/2 combination)
MCH	Potassium	Nitrites	Stool sample ^e
MCHC	Chloride	Leukocyte esterase	
Platelet count	Total CO ₂ (bicarbonate)	Urobilinogen	
WBC count	AST, ALT	Urine bilirubin	
CD4+ count	Total bilirubin	Microscopy ^a	
Total neutrophils (Abs)	Alkaline phosphatase		
Eosinophils (Abs)	Creatine kinase		
Monocytes (Abs)	Uric acid		
Basophils (Abs)	Albumin		
Lymphocytes (Abs)	Total cholesterol (fasting)		
Reticulocytes (%)	LDL-C (fasting)		
	HDL-C (fasting)		
	Triglycerides (fasting)		
	Total protein		
	PT/INR		
	Additional Tests^f (potential Hy's Law)		Immunogenicity, PD and other Biomarker Tests
	AST, ALT (repeat)		ADA
	Total bilirubin (repeat)		nAb ^g
	Albumin (repeat)		pSTAT3 (predose [trough] samples only, in Phase 2)
	Alkaline phosphatase (repeat)		Total IgG & IgM
	Direct bilirubin		Plasma CCI
	Indirect bilirubin		Plasma CCI & CCI
	GGT		Whole blood for leukocyte immunophenotype and RNA
			CCI
			CCI
			Antibodies CCI
			CRP
			Direct Coomb's test ^h

Abbreviations: Abs = absolute; ADA = anti-drug antibody; ALT = alanine aminotransferase; CCI; CCI; AST = aspartate aminotransferase; BUN = blood urea nitrogen; C = complement; CD4+ = cluster of differentiation 4; CRP = C-reactive protein; dsDNA = double-stranded deoxyribonucleic acid;; FSH = follicle stimulating hormone; GGT = gamma-glutamyltransferase; HDL-C = high-density lipoprotein cholesterol; HIV = human immunodeficiency virus; IgG = immunoglobulin G; IgM = immunoglobulin M; INR = international normalized ration; IL-21 = interleukin 21; LDL-C = low-density lipoprotein cholesterol; MCH = mean corpuscular hemoglobin; MCHC = mean corpuscular hemoglobin concentration; MCV = Mean corpuscular volume; nAb = neutralizing antibody; pSTAT3 = phosphorylated signal transducer and activator of transcription 3; PT = prothrombin time; qual = qualitative; RBC = red blood cell; RDW = RBC distribution width; RNA = ribonucleic acid;

Table 3. Laboratory Tests

Hematology	Chemistry	Urinalysis	Other Safety Tests
RNP = ribonucleoprotein; SAE = serious adverse event; SC = subcutaneous; CCI [REDACTED]; TB = tuberculosis.			
a. On all urine samples.			
b. At screening only, in women who are amenorrheic for at least 12 consecutive months and under 55 years old.			
c. For WOCBP.			
d. Screening only.			
e. At screening, and if a patient develops diarrhea during the study a stool sample must be provided to test for ova, parasites, and cryptosporidium.			
f. Additional testing for potential Hy's Law cases only (See Section 7.2.2.6.3).			
g. If patient is positive for ADA.			
h. If clinically indicated.			

7.2.1.1 Pregnancy testing

For WOCBP, a serum pregnancy test will be performed at screening. Following a negative serum pregnancy result at screening, appropriate contraception must be commenced or continued and a further negative urine pregnancy test results will then be required at the baseline visit before the patient may receive the investigational product. Urine pregnancy tests will also be routinely repeated at study drug administration visits prior to study drug administration, and additionally whenever 1 menstrual cycle is missed or when potential pregnancy is otherwise suspected. In the case of a positive pregnancy test or confirmed pregnancy, the patient will be discontinued from study drug, an EOT visit should be performed (Day 180), and a last follow-up visit 90 days after last dose should be scheduled (Day 270). Safety follow-up visit procedures based on the Schedule of Assessments (see [Section 6.4](#)).

See [Section 7.2.2.7.1](#) for information on reporting of pregnancies as AEs/SAEs during the study.

7.2.1.2 Tuberculosis Screening

During the screening period, it must be determined and documented that a patient does not have evidence of active or latent or inadequately treated TB per the exclusion criteria ([Section 5.5](#)). The results of TB screening, which includes the QuantiFERON[®]-TB Gold In-Tube (QFT-G) test and a chest x-ray, conducted in the 3 months prior to screening or during the screening period must be documented in study records prior to randomization (Day 0).

7.2.1.2.1 *Mycobacterium Tuberculosis Testing Using QuantiFERON Test⁴⁰*

QuantiFERON[®]-TB Gold In-Tube (QFT-G) is an in vitro diagnostic test using a peptide cocktail simulating ESAT-6, CFP-10, and TB 7.7 proteins to stimulate cells in heparinized whole blood. Detection of INF γ performed by enzyme-linked immunosorbent assay (ELISA) is used to identify in vitro responses to these peptide antigens that are associated with Mycobacterium tuberculosis infection. QFT-G is an indirect test for M. tuberculosis infection (including disease) and is intended for use in conjunction with risk assessment, radiography and other medical and diagnostic evaluations.

Test results will be reported as positive, negative, or indeterminate. A negative QFT-G test result is required to meet the inclusion criterion. In the case of an indeterminate result, repeat tests should be permitted for the purpose of determining eligibility of patients to enroll in this study. If a repeat test is indeterminate again, the patient is a screen failure. The procedure for using this test and interpreting the results will be described fully in the laboratory manual, which will be provided to investigators.

7.2.2 Adverse Events

7.2.2.1 Definitions

An AE is defined as any untoward medical occurrence experienced by a study patient, whether or not considered drug related by the principal investigator.

AEs are unfavorable changes in a general condition, subjective or objective signs or symptoms, worsening of pre-existing concomitant disease, and clinically significant abnormality in laboratory parameters observed in a patient in the course of a clinical study.

Non-serious SLE manifestations or abnormal laboratory results related to SLE disease activity would not be recorded as AEs unless they meet the definition for SAEs ([Section 7.2.2.5](#)).

7.2.2.2 Recording of Adverse Events

AEs should be collected and recorded for each patient from the date of the first dose of study drug until the end of their participation in the study, including the safety follow up period.

AEs may be volunteered spontaneously by the study patient, or discovered by the study staff during physical examinations or by asking an open, nonleading question such as ‘How have you been feeling since you were last asked?’ All AEs and any required remedial action will be recorded on the Adverse Events eCRF and Safety Adverse Event Form. The details of the AE, date of AE onset (and time, if known), date of AE outcome (and time, if known), and action taken for the AE will be documented together with the principal investigator’s assessment of the seriousness of the AE and causal relationship to the study drug and/or the study procedure.

All AEs should be recorded individually, using diagnostic terms where possible. If the diagnosis is not established, individual symptoms may be reported. The AEs will subsequently be coded using the Medical Dictionary for Regulatory Activities (MedDRA).

7.2.2.3 Severity of Adverse Events

Each AE will be assessed by the principal investigator according to the National Cancer Institute Common Terminology Criteria for Adverse Events (NCI CTCAE), version 4.03 criteria.⁴¹ When changes in the severity (grade) of an AE occur more frequently than once a day, the maximum severity for the event should be noted for that day. Any change in severity of signs and symptoms over a number of days will be captured by recording a new AE, with the amended severity grade and the date (and time, if known) of the change.

7.2.2.4 Causality of Adverse Events

The principal investigator will assess the causal relationship between BOS161721 or placebo and the AE. One of the following categories (Table 4) should be selected based on medical judgment, considering the definitions below and all contributing factors.

Related	A clinical event, including laboratory test abnormality, occurs in a plausible time relationship to treatment administration and which concurrent disease or other drugs or chemicals cannot explain. The response to withdrawal of the treatment (dechallenge ^a) should be clinically plausible. The event must be definitive pharmacologically or phenomenologically, using a satisfactory rechallenge ^b procedure if necessary.
Unrelated	A clinical event, including laboratory test abnormality, with little or no temporal relationship with treatment administration. May have negative dechallenge and rechallenge information. Typically explained by extraneous factors (eg, concomitant disease, environmental factors, or other drugs or chemicals).

^a Dechallenge: Upon discontinuation of a drug suspected of causing an AE, the symptoms of the AE disappear partially or completely, within a reasonable time from drug discontinuation (positive dechallenge), or the symptoms continue despite withdrawal of the drug (negative dechallenge). Note that there are exceptions when an AE does not disappear upon discontinuation of the drug, yet drug relatedness clearly exists (for example, as in bone marrow suppression, fixed drug eruptions, or tardive dyskinesia).

^b Rechallenge: Upon re-administration of a drug suspected of causing an AE in a specific patient in the past, the AE recurs upon exposure (positive rechallenge), or the AE does not recur (negative rechallenge).

An unexpected adverse drug event is any adverse drug event for which the specificity or severity is not consistent with the current IP.

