6.2.2.7.1 Reporting of Pregnancy

As information is available, a pregnancy diagnosed during the study will be reported within 24 hours to the sponsor via the Pregnancy Notification and Outcome Form, including pregnancy in female patients who received study drug and female partners of male study patients who received study drug. The pregnancy should be followed to term and/or outcome and this outcome should also be reported to the sponsor via the Pregnancy Notification and Outcome Form. Pregnancy itself is not regarded as an AE or SAE unless there is complication.

In the case of a live birth, the structural integrity of the neonate can be assessed at the time of birth. In the event of a termination, the reason(s) for termination should be specified and, if clinically possible, the structural integrity of the terminated fetus should be assessed by gross visual inspection (unless pre-procedure test findings are conclusive for a congenital anomaly and the findings are reported).

If the outcome of the pregnancy meets the criteria for an AE or SAE (ie, ectopic pregnancy, spontaneous abortion, intrauterine fetal demise, neonatal death, or congenital anomaly [in a live born, a terminated fetus, an intrauterine fetal demise, or a neonatal death]), the investigator should follow the procedures for reporting SAEs.

Additional information about pregnancy outcomes that are reported as SAEs follows:

- Spontaneous abortion includes miscarriage and missed abortion
- Neonatal deaths that occur within 1 month of birth should be reported, without regard to causality, as SAEs. In addition, infant deaths after 1 month should be reported as serious adverse events when the investigator assesses the neonatal death as related or possibly related to exposure to investigational product.

6.2.2.7.2 *Reporting of Serious Adverse Events*

The principal investigator is responsible for providing notification to the sponsor of any SAE via the Safety Adverse Event Form, whether deemed study drug related or not, that a patient experiences during their participation in this study within 24 hours of becoming aware of the event.

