If an SAE is fatal or life threatening, notification to the sponsor must be made aware immediately, irrespective of the extent of available AE information. This timeframe also applies to additional new information (follow-up) on previously forwarded SAE reports as well as to the initial and follow-up reporting of exposure during pregnancy and exposure via breastfeeding cases. In the rare event that the investigator does not become aware of the occurrence of an SAE immediately (eg, if an outpatient study patient initially seeks treatment elsewhere), the investigator is to report the event within 24 hours after learning of it and document the time of his/her first awareness of the AE.

The principal investigator will review each SAE and evaluate the intensity and the causal relationship of the event to the study drug. All SAEs will be recorded from the time of first dose of study drug through the safety follow-up period (up to Day 270). SAEs occurring after the final follow-up visit and coming to the attention of the principal investigator must be reported only if there is (in the opinion of the principal investigator) reasonable causal relationship with the study drug.

As a minimum requirement, the initial notification should provide the following information:

- Study number
- Patient number
- Details of the SAE (verbatim details are sufficient for immediate notification)
- Criterion for classification as ‘serious’
- Causality assessment (which may be updated in a follow-up report when sufficient information is available to make this classification)

Initial reports of SAEs must be followed later with detailed descriptions, including clear photocopies of other documents as necessary (eg, hospital reports, consultant reports, autopsy reports, etc), with the study patient’s personal identifiers removed. All relevant information obtained by the principal investigator through review of these documents will be recorded and submitted to the sponsor within 24 hours of receipt of the information. If a new Safety Adverse Event Form is submitted, then the principal investigator must sign and date the form. The sponsor may also request additional information on the SAE, or clarification of omitted or discrepant information from the initial notification, which the principal investigator or an authorized delegate should submit to the sponsor within 24 hours of the request as possible.

6.2.2.7.3 *Reporting of Adverse Events of Special Interest*

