8.2.5 Analysis of Safety

8.2.5.1 Safety Analysis

Safety analyses will be performed on the SS. AE data will be coded to system organ class and preferred term using MedDRA. The number and percentage of patients experiencing any treatment-emergent AE, overall, and by system organ class an preferred term, will be tabulated. Treatment-emergent AEs will also be summarized by severity and relationship.

Concomitant medications will be coded using the WHO Drug dictionary. Observed values and changes from baseline in vital signs, ECG readings, and hematology and clinical chemistry parameters will be summarized at each individual visit.

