4.1.1.2 Dose Limiting Toxicity (DLT)

Severity of adverse events will be graded according to National Cancer Institute Common Terminology Criteria for Adverse Events (NCI CTCAE) version 4.03. For the purpose of dose escalation, any of the following AEs occurring after study drug administration, which are attributable to the study drug, will be considered DLTs:

Hematologic:

- Grade 4 neutropenia
- Grade 3 neutropenic infection
- Grade 3 thrombocytopenia with bleeding
- Grade 4 thrombocytopenia

Non-Hematologic:

- Grade 3 or above toxicities, persisting after optimal treatment with standard medical therapy (eg, anti-emetics, anti-diarrheals)
- Drug-induced liver injury ([DILI], Hy's Law), as defined in [Section 7.2.2.6.3](#)

Investigators should always manage their patients according to their medical judgment which may include interruption of study drug based on the particular clinical circumstances.

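### The two causality categories in Table 4 leave no place for an event with plausible timing and a possible other cause, so related AEs, and perhaps DLTs, may be undercounted

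*Protocol*

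**What the plan says.** Section 7.2.2.4 asks the principal investigator to place each AE in one of two categories. The choice "should be selected based on medical judgment, considering the definitions below and all contributing factors".

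- **Related.** The event "occurs in a plausible time relationship to treatment administration and which concurrent disease or other drugs or chemicals cannot explain". The response to withdrawal should be clinically plausible. In addition, "The event must be definitive pharmacologically or phenomenologically, using a satisfactory rechallenge" procedure where one is needed.
- **Unrelated.** The event is one "with little or no temporal relationship with treatment administration". The entry adds that such events are typically explained by extraneous factors.

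Three other places depend on a causal judgement:

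- Section 4.1.1.2 (DLT): "any of the following AEs occurring after study drug administration, which are attributable to the study drug, will be considered DLTs". Section 4.1.1.3 halts further dosing in a cohort at two or more DLTs.
- Section 8.2.5.1: "Treatment-emergent AEs will also be summarized by severity and relationship". The Phase 1b primary safety endpoints, as revised in V3.0, also include related AEs and AEs by relatedness.
- Section 6.2.2.7.1 speaks of infant deaths "related or possibly related to exposure to investigational product", and Section 6.2.2.7.2 speaks of late SAEs with a "reasonable causal relationship with the study drug".

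Table 4 and the DLT section are available only in the reprinted V1.0 and V2.0 (Amendment 1) texts. Table 4 reads the same in both. The V3.0 summary of changes lists no change to either, but it covers significant changes only.

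**The concern.** A two-category scale works only if every event belongs in one of the categories. Here the exclusion of other causes in Related is firm, and the timing condition in Unrelated is firm. The events between them have no home. Investigators will have to improvise, and may do so differently.

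The wording also leans one way. Related rules out an event that disease or another drug could explain, while the last line of Unrelated names such explanations as typical. An investigator following the text closely is more likely to choose Unrelated. That lowers the related-AE rates. If the DLT section relies on the same scale, it also lowers the count that governs cohort halting, in the direction that favours escalation.

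**Working it through.** The plan states no DLT rate, attribution rate or operating characteristic for the halting rule, so there is no figure to reproduce. The check is mainly textual.

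**1. The definitions side by side**

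| Aspect | Related | Unrelated |
|---|---|---|
| Timing | plausible | little or none |
| Other causes | must be unable to explain the event | typically explain it |
| Withdrawal | response should be plausible | may be negative |
| Certainty | definitive, by rechallenge if needed | no condition |

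**2. Are they exhaustive?** Cross timing with the presence of another possible cause:

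- Plausible timing, no other cause: Related, if also definitive.
- Plausible timing, another possible cause: fails Related on other causes and fails Unrelated on timing.
- Little or no temporal relationship: Unrelated.

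The second case is uncovered. So is an event with plausible timing and no other cause that is not definitive.

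**3. Example.** Grade 4 neutropenia begins 10 days after the second dose, and the investigator regards background azathioprine as a possible cause. The timing keeps it out of Unrelated and the possible other cause keeps it out of Related.

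**4. Is the uncovered case likely here?** All patients have active SLE. Inclusion criterion 8 requires a permitted steroid-sparing agent or prednisone. Exclusion criteria 16 and 17 tolerate lower platelets and hemoglobin when SLE is the cause. Competing explanations will be common, but the documents do not allow a count.

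**5. What under-attribution would do to the halting rule (illustration, assumed rates).** Let *n* be the active patients in a cohort (5 in Cohort 1, 9 each in Cohorts 2 and 3), *p* the true per-patient DLT rate, *f* the share judged attributable, and *q* = *p* × *f*. With at most one DLT per patient:

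P(at least 2 counted) = 1 − (1 − q)^n − n·q·(1 − q)^(n−1)

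For n = 9, p = 0.30, f = 1: 1 − 0.7^9 − 9 × 0.3 × 0.7^8 = 1 − 0.040 − 0.156 = 0.804.

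For f = 0.25, q = 0.075: 1 − 0.925^9 − 9 × 0.075 × 0.925^8 = 1 − 0.496 − 0.362 = 0.142.

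| n | p (assumed) | f = 1 | f = 0.5 | f = 0.25 | f = 0.1 |
|---|---|---|---|---|---|
| 9 | 10% | 22.5% | 7.1% | 2.0% | 0.3% |
| 9 | 20% | 56.4% | 22.5% | 7.1% | 1.3% |
| 9 | 30% | 80.4% | 40.1% | 14.2% | 2.8% |
| 9 | 40% | 92.9% | 56.4% | 22.5% | 4.8% |
| 5 | 30% | 47.2% | 16.5% | 4.8% | 0.8% |

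Both *p* and *f* are assumptions. The table shows that the count is sensitive to attribution. It does not show what attribution will be.

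**The case against.** The strongest reply is that Table 4 is not applied mechanically. The category is chosen on medical judgement with all contributing factors in view, and an investigator may decide that a long-stable background drug does not explain a new event. Criterion 8 requires at least 12 weeks of use and 56 days at a stable dose for the steroid-sparing agents. Rechallenge is asked for only if necessary. Footnote a accepts that relatedness can be clear even when an event does not resolve on withdrawal, and names bone marrow suppression, so the withdrawal condition carries little weight here. All of this stands. It makes the outcome uncertain, but it does not supply the missing category.

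A reader might infer more: that events with any alternative explanation cannot qualify as Related, that every hematologic DLT has such an explanation, and that DLTs will almost never be counted. The documents do not support this.

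- The judgement clause leaves room to classify such events as Related.
- The DLT section does not cite Table 4, and detailed escalation criteria sit in the DMC Charter. The link from attributable to Related is an inference.
- The white cell and neutrophil entry limits (exclusion criteria 13 and 14) carry no SLE allowance.
- Criterion 8 can be met with an antimalarial or prednisone alone, so not every patient is on a cytotoxic immunosuppressant.

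Nor does the protocol already hold a general standard of reasonable possibility for SAEs. The phrase in Section 6.2.2.7.2 covers only SAEs after the final follow-up visit, and the one in Section 6.2.2.7.1 covers only infant deaths after one month.

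There are also backstops. The DMC sees unblinded data and may recommend termination for any safety concern (Section 9.2), SAEs are reported whatever their causality (Section 6.2.2.7.2), and all treatment-emergent AEs are tabulated (Section 8.2.5.1). These limit the harm but do not correct the related-AE tables or define the DLT count.

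**Conclusion.** The point holds as a defect of definition. The two categories are not exhaustive, Related is restrictive, and other sections use causal terms that the scale lacks. Related-AE summaries may be understated. DLTs may be undercounted on the condition that attributable is read as Table 4 Related. The direction favours escalation, but the size cannot be derived from the documents.

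The conclusion also assumes that the V2.0 wording of Table 4 and of the DLT section carries over into V3.0. That is likely, since no change is listed, but it has to be confirmed in current Section 6.2.2.4 and the current DLT section.

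**What to change.** Reword Table 4 so that every event falls in exactly one category: Related when a causal relationship with study drug is reasonably possible, Unrelated otherwise. Drop from Related the requirement that other causes be unable to explain the event, and the definitive and rechallenge conditions.

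Reconcile the attribution wording in the DLT section, and the causal terms in Sections 6.2.2.7.1 and 6.2.2.7.2, with the revised table. The list of DLTs and the halting threshold remain with the sponsor.

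The cost is protocol wording and eCRF guidance. More events will be reported as related, so the related-AE rates will look less favourable.
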